8.1.3. DEFINITION OF ADVERSE DEVICE EFFECT (ADE) AND SERIOUS ADVERSE DEVICE EFFECT (SADE)

An Adverse Device Effect (ADE) is defined as any untoward or unintended response to a medical device. This definition includes any event resulting from insufficiencies or inadequacies in the instructions for use or the deployment of the device. This definition also includes any event that is a result of user error. A Serious Adverse Device Effect (SADE) is an adverse device effect that has resulted in any of the consequences characteristic of a serious adverse event or that might have led to any of these consequences if suitable action had not been taken or intervention had not been made or if circumstances had been less opportune. All SADEs must immediately and without delay (within 24 hours) be reported to the study Sponsor by fax and/or email.

8.1.4. DEFINITION OF UNANTICIPATED ADVERSE DEVICE EFFECT (UADE)

An unanticipated adverse device effect (UADE) is defined as any serious adverse effect on health or safety or any life-threatening problem or death caused by, or associated with, a device, if that effect, problem, or death was not previously identified in nature, severity, or degree of incidence in the investigational plan or application (including a supplementary plan or application), or any other unanticipated serious problem associated with a device that relates to the rights, safety, or welfare of subjects (21 CFR 812.3(s)). All UADEs must immediately and without delay (within 24 hours) be reported to the study Sponsor by fax and/or email.

8.2. CLASSIFICATION OF AN ADVERSE EVENT

8.2.1. SEVERITY OF EVENT

The following guidelines will be used to describe the severity of an event:

- **Mild** – Awareness of the event, may cause no or minimal interference with the subject's daily life.
- **Moderate** – Discomfort enough to cause a noticeable impact on the subject's daily life.
- **Severe** – Incapacitation or significant impact on the subject's daily life.

8.2.2. RELATIONSHIP TO STUDY DEVICE/PROCEDURES

Two types of relationships will be assessed:

1. Related to the Latera device or Latera device-specific procedure, including Implant delivery
2. Related to turbinate reduction procedure

The procedure-trained Investigator's assessment of an AE's relationship to the study device or implant procedure and/or the concomitant procedure is part of the documentation process, but it is not a factor in determining what is or is not reported in the study. If there is any doubt as to whether a clinical observation is an AE, the event must be reported. All AEs must have their relationship to the Latera study device or Latera device procedure assessed.

For all collected AEs, the Investigator who examines and evaluates the subject will determine the AE's causality based on temporal relationship and his/her clinical judgment. The degree of certainty about causality will be graded using the categories below.

- **Definitely Related** – The event is definitely related to the study device/procedure or concomitant procedure
- **Probably Related** – The event is probably related to the study device/procedure or concomitant procedure; or the event cannot be explained by other condition or illness.
- **Possibly Related** – The event is possibly related to the study device/procedure or concomitant procedure, but not likely.
- **Unlikely Related** – The event is unlikely related to the study device/procedure or concomitant procedure.
- **Not Related** – The event is definitely not related to the study device/procedure or concomitant procedure.

SPACE LEFT INTENTIONALLY BLANK

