4.2. STUDY ENDPOINTS

4.2.1. PRIMARY ENDPOINTS

Primary Efficacy Endpoint: Proportion of treatment responders at 6 months post procedure.

- A responder is defined as a subject that has at least 1 NOSE class improvement or at least 20% NOSE score reduction.

Primary Safety Endpoint: Nasal procedure and Latera device-related adverse events through 6 months.

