8. ASSESSMENT OF SAFETY

8.1. SPECIFICATION OF SAFETY PARAMETERS

All Serious Adverse Events (SAE), Adverse Device Effect (ADE) and Serious Adverse Device Effects (SADE) will be collected and documented through the end of subject participation in the study. In addition, all non-serious device and procedure-related Adverse Events (AE) and all non-serious head and neck, and/or respiratory related AEs will also be collected and documented.

The primary safety endpoint evaluation will consider nasal procedure related and Latera related adverse events through 6 months post-procedure.

The following information for each AE, ADE, SAE and SADE will be collected:

- Date of onset
- Status and/or Outcome
- Date of resolution
- Adverse Event/Effect type (See Section 8.1.1)

In the event of Implant loss or removal, the following information will be documented:

- Implant exposed intranasal at pierce point or exposed on the external skin surface
- Implant retrieved by surgeon or subject
- Whether Implant loss or removal was complete or partial
- SAE or SADE (See Section 8.1.2 and 8.1.3)
- Severity of event (See Section 8.2.1)
- Relation to Study Device and/or procedure (See Section 8.2.2)
- Action taken
- Descriptive narration of Event/Effect

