10.4.4. SAFETY ANALYSES

Two analysis sets will be used to summarize adverse events. The ITT analysis set will be used to summarize acute adverse events (through 1 month post procedure), and the mITT analysis set will be used to summarize adverse events over the entire duration of follow-up. The primary safety reporting time-point is 6 months post-implant.

The overall incidence (i.e., number and percent of subjects with 1 or more adverse event) of adverse events, serious adverse device events, serious adverse events, fatal adverse events, and device related events (e.g., possibly, probably or definitely related) will be calculated for the acute phase, through 6 months post-procedure and for the entire duration of follow-up. The overall incidence of mild, moderate and severe events will be calculated by considering the most severe event for each subject.

In addition, the overall incidence for each adverse event type will be calculated. The adverse event types will be classified as defined in section 8.1.1

The implant retrieval rate will be calculated based on the number of implants retrievals per the total number of implants placed.

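### The Possibly Related and Unlikely Related grades in section 8.2.2 overlap, and the device-related cut-off in section 10.4.4 falls between them

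*Combined protocol and SAP*

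**What the plan says.** The primary safety endpoint (section 4.2.1) is "Nasal procedure and Latera device-related adverse events through 6 months". Section 8.1 repeats it: "The primary safety endpoint evaluation will consider nasal procedure related and Latera related adverse events through 6 months post-procedure". Neither place says which causality grades make an event related.

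Section 8.2.2 provides five grades. The third is defined as "The event is possibly related to the study device/procedure or concomitant procedure, but not likely" and the fourth as "The event is unlikely related to the study device/procedure or concomitant procedure". On who assigns the grade, it says that "the Investigator who examines and evaluates the subject will determine the AE's causality based on temporal relationship and his/her clinical judgment".

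The only cut-off is in section 10.4.4, which plans incidences for several classes of event, among them "device related events (e.g., possibly, probably or definitely related) will be calculated for the acute phase, through 6 months post-procedure" and for the whole of follow-up. Unlikely Related and Not Related are absent from that list.

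**The concern.** An endpoint made up of related events is only as well defined as the line between related and not related. Here that line is drawn between two grades whose definitions say the same thing in different words. Two investigators who hold the same opinion of the same event can grade it differently, both within the protocol, and one event is counted while the other is not.

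What is at stake is the reported related-event incidence through 6 months and its consistency across about 25 sites. The secondary endpoint of procedure- and device-related events through 24 months depends on the same scale. The study is open label (section 10.6). The Medical Monitor judges expectedness (8.2.3) and reviews adverse events periodically (8.6), but no adjudication of causality is described that would even out different readings.

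**Working it through.** The plan gives no expected related-event rate, safety threshold or safety power figure, so there is no planned number to reproduce. The check compares the text, followed by one line of arithmetic.

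**Step 1. Set the scale beside the cut-off.**

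| Grade (8.2.2) | What the definition adds to the label | Listed as device related in 10.4.4 |
|---|---|---|
| Definitely | nothing | yes |
| Probably | or no other condition or illness explains the event | yes |
| Possibly | but not likely | yes |
| Unlikely | nothing | no |
| Not related | definitely not | no |

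**Step 2. Test exclusivity.** Take an event that the investigator thinks could be related but is not likely to be. It meets the Possibly definition in full. It also meets the Unlikely definition, which asks only that a relation be unlikely. Section 8.2.2 names temporal relationship and clinical judgment as the general basis for grading but attaches no such criterion to either grade, so nothing in the text settles the choice.

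**Step 3. Ask which confusions change the count.** Definitely versus Probably does not, because both are listed. Unlikely versus Not Related does not, because neither is listed. Possibly versus Unlikely does.

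**Step 4. Check the other half of the endpoint.** Section 8.2.2 assesses two relationships: to the Latera device or its placement procedure, and to turbinate reduction. The list in 10.4.4 is attached to device-related events and introduced by *e.g.* No cut-off is stated for procedure-related events, so for that part of the endpoint the boundary is not set at all.

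**Step 5. Size per subject.** Section 10.5 gives 150 subjects with 6-month follow-up and up to 170 enrolled. If *k* subjects have as their only qualifying event one that crosses the line, the incidence moves by *k*/*N*:

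- *N* = 150: 1/150 = 0.67 percentage points per subject
- *N* = 170: 1/170 = 0.59 percentage points per subject

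The documents give no basis for *k*, so the total effect cannot be stated.

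**The case against.** Five points can be made on the other side.

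- **The labels are ordered.** Read in sequence, *not likely* can be taken as not probable, which marks Possibly off from the grade above it. This is a fair reading, and it disposes of a stronger inference: that the scale has a hole between Probably and Possibly, where a plausible relation has no home. The documents do not establish such a hole. The reading does not repair the lower boundary, because an event that is not probable may still be either Possibly or Unlikely.
- **The cut-off is only illustrative.** Sections 4.2.1 and 8.1 set none, and 10.4.4 gives one only as an example and only for device-related events. A reader might infer that the boundary between Possibly and Unlikely fixes membership of the whole primary safety endpoint. That goes too far: it is indicated for the device part and unstated for the procedure part. An unstated cut-off is itself something to correct.
- **An outer bound is already planned.** Section 10.4.4 reports the incidence of all adverse events through 6 months, so an event graded Unlikely still appears there. This stands, but that bound is loose because it includes events graded Not Related.
- **Nothing inferential depends on it.** Section 10.2 states no formal hypothesis beyond the primary efficacy one, the halting rules in 8.5 use no related-event rate, and with one arm there is no between-arm comparison to bias. This stands. A reader who infers an effect on type I error or power would be wrong.
- **Causality does not govern reporting.** Section 8.2.2 says of the relationship assessment that "it is not a factor in determining what is or is not reported in the study". That concerns whether an event is recorded, not whether it is counted as related afterwards.

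A reader might also infer that the operator chooses what to count. Section 8.2.2 assigns causality to the investigator who examines the subject, and 8.4.1 requires the procedure-trained investigator to approve the adverse event source documents. The documents support dependence on individual judgment. They do not show that it would lean in one direction.

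**Conclusion.** The point holds as a defect in a stated rule. Possibly Related and Unlikely Related are not mutually exclusive, the cut-off in 10.4.4 lies between them for device-related events, and no cut-off is given for procedure-related events. The descriptive primary safety incidence through 6 months therefore depends partly on how each investigator reads the scale.

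The size is about 0.6 to 0.7 percentage points for each subject whose only qualifying event crosses the line, assuming a denominator between 150 and 170. The total and its direction are unknown. The conclusion rests on reading *not likely* and *unlikely* as equivalent, and on taking the 10.4.4 list as the intended rule despite its *e.g.* It is worth correcting because the endpoint is a primary one and the correction is cheap.

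**What to change.** 1. **Section 8.2.2.** Delete *but not likely* and make the two grades exclusive without narrowing Possibly. For example, Possibly: a relation cannot reasonably be excluded, even if another cause is more plausible. Unlikely: timing or mechanism makes a relation improbable and another cause explains the event. A definition of Possibly that required the alternative cause to be only equally plausible should be avoided. It would push possible events with a likelier alternative cause down to Unlikely and could lower the headline count.
2. **Section 10.4.4.** Drop *e.g.* and state that possibly, probably and definitely related events count as related, for both device- and procedure-related events.
3. **Section 10.4.4 or the SAP.** Add one sensitivity row that also counts events graded unlikely related. It uses grades already collected, and section 10.1 leaves the SAP open until database lock.

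The cost is a wording change and one table row. The sensitivity incidence will be equal to or higher than the headline. If enrolment has begun, the new definitions should apply only going forward, and the extra row covers events graded under the present wording.

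The row bounds recorded events only. Section 8.1 collects non-serious events outside the head, neck and respiratory system only when related, and section 8.3 records worsening of a baseline condition only when related. An event that was never recorded for that reason cannot be recovered by the row.

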8.2.3. EXPECTEDNESS

The Medical Monitor will be responsible for determining whether an AE is expected or unexpected. An AE will be considered unexpected if the nature, severity, or frequency of the event is not consistent with the risk information previously described for the device as well as the concomitant turbinate reduction procedure.

Refer to section 2.3.2 for list of expected risks.

8.3. TIME PERIOD AND FREQUENCY FOR EVENT ASSESSMENT AND FOLLOW-UP

The occurrence of an AE or SAE may come to the attention of study personnel during study visits and interviews of a subject presenting for medical care, or upon review by a study monitor.

All SAEs and all device and procedure-related AEs, including local and systemic reactions not meeting the criteria for SAEs, as well as all AEs related to head/neck and respiratory conditions occurring during the course of the study will be captured on the appropriate CRF.

Information to be collected includes event description, time of onset, Investigator's assessment of severity, relationship to study product (assessed only by those with the training and authority to make a diagnosis) or concomitant procedures, and time of resolution/stabilization of the event.

All SAEs and AEs will be followed to adequate resolution, or through the twenty-four month follow up visit.

Any medical condition that is present at the time of the participant's procedure will be considered as a baseline condition or comorbidity, and will not be reported as an AE. However, if the subject's condition deteriorates at any time during the study, and the condition is procedure/device related, it will be recorded as an AE. AEs will be recorded in the data collection system throughout the study.

Changes in the severity of an AE will be documented. AEs characterized as intermittent require documentation of onset and duration of each episode.

At each study visit, the Investigator will inquire about the occurrence of AE/SAEs since the last visit. Events will be followed for outcome information until resolution or stabilization.

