8.1.2. DEFINITION OF ADVERSE EVENTS (AE) AND SERIOUS ADVERSE EVENTS (SAE)

An adverse event (AE) or effect is defined as any untoward and unintended medical occurrence experienced by a clinical study subject. An AE can therefore be any unfavorable and unintended sign, symptom, or disease temporally associated with the use of the investigational product, whether or not related to the product.

The following events will be considered to be serious adverse events (SAE) and must immediately and without delay (within 24 hours) be reported to the study Sponsor by fax and/or email. These events must be reported whether or not the Investigator believes they are related to study procedures, activities or device:

- Death (the investigator will provide a copy of any post-mortem findings, including histopathology reports if available).
- Life-threatening event or injury
- Disability – significant, persistent, or permanent change, impairment, or damage or disruption in the subject's body function/structure, physical activities or quality of life
- Necessitate immediate medical or surgical intervention to:
 - Preclude permanent impairment of a body function or permanent damage to a body structure; or
 - Relieve unanticipated temporary impairment or damage.
- Prolongation of a hospitalization
- Require new hospitalization

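### Section 8.3 records worsening of a baseline condition as an AE only if it is judged related, which contradicts 8.1, 8.1.2 and 8.2.2 and drops non-serious head/neck and respiratory worsening judged unrelated

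*Combined protocol and SAP*

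**What the plan says.** Section 8.3 starts from a default: a medical condition present at the procedure "will be considered as a baseline condition or comorbidity, and will not be reported as an AE". The exception that follows has two joint requirements. If the subject's "condition deteriorates at any time during the study, and the condition is procedure/device related, it will be recorded as an AE".

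Four other provisions bear on the same events:

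- Section 8.2.2 says of the investigator's relatedness assessment that "it is not a factor in determining what is or is not reported in the study", and adds: "If there is any doubt as to whether a clinical observation is an AE, the event must be reported".
- Section 8.1.2 defines an AE as an unfavourable occurrence "temporally associated with the use of the investigational product, whether or not related to the product". For serious events it says: "These events must be reported whether or not the Investigator believes they are related to study procedures, activities or device".
- Section 8.1 says that "all non-serious head and neck, and/or respiratory related AEs will also be collected and documented". An earlier paragraph of 8.3 likewise requires head/neck and respiratory AEs to be captured, with no relatedness condition.
- Section 10.4.4 plans the incidence of all AEs, of device-related AEs, by severity and by event type. The primary safety endpoint in 4.2.1 is narrower: "Nasal procedure and Latera device-related adverse events through 6 months".

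**The concern.** The 8.3 sentence puts a causality judgement ahead of capture. The treating investigator, who knows the treatment because the study is single-arm and open-label (10.6), decides whether a worsening is related. Only if the answer is yes does an AE record exist.

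The rule reaches the disease under study. Inclusion criterion 5 requires nasal airway obstruction due to nasal valve collapse, so every subject carries a baseline condition of the nose. Section 2.3.2 lists oedema with later obstruction as a risk of turbinate reduction, so a listed procedural harm can look like worsening of what the subject already had. Sites that follow 8.3 and sites that follow 8.2.2 would record the same event differently, and about 25 sites are planned.

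**Working it through.** No arithmetic applies: the question is what the text tells a site to record. The documents give no rate for worsening of baseline conditions.

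**Step 1. Is the 8.3 exception exclusive?** The word *only* does not appear. However, the default is that the condition is not reported, and the single exception needs both deterioration and relatedness. The effect is that deterioration judged unrelated stays under the default.

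**Step 2. Compare the instructions by type of worsening, through month 12.**

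| Worsening of a baseline condition | 8.3 baseline sentence | Other provisions | Result |
|---|---|---|---|
| Serious, judged unrelated | Not an AE | Reportable (8.1, 8.1.2, the SAE paragraph of 8.3, 8.4.2) | Conflicting instruction |
| Non-serious, head/neck or respiratory, judged related | Recorded | Collected (8.1, 8.3) | Consistent |
| Non-serious, head/neck or respiratory, judged unrelated | Not an AE | Collected (8.1, 8.3), supported by 8.1.2 and 8.2.2 | Clear loss if the baseline sentence is followed |
| Non-serious, other system, judged related | Recorded | Collected (8.1, 8.3) | Consistent |
| Non-serious, other system, judged unrelated | Not an AE | Outside the scope of 8.1 | No loss against the planned scope |

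**Step 3. After month 12.** Section 7.1.5 limits collection to adverse device effects. If it governs, non-serious worsening judged unrelated is out of scope anyway, so the loss runs to month 12.

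**Step 4. Which analyses are affected?** The events in the third row are missing from the overall AE incidence, the severity incidences and the type incidences of 10.4.4. They do not belong in the primary safety endpoint if the judgement of unrelated is correct. If it is wrong, the event should have counted, but there is no AE record.

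**Step 5. Is the filter itself well defined?** Section 8.2.2 has five grades of relatedness, and 10.4.4 counts possibly, probably and definitely related events. Section 8.3 does not say which grades pass. Its wording also asks whether the condition is related, not whether its deterioration is. A condition that predates the procedure can hardly meet that test literally.

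**Step 6. Reach.** The rule applies to up to 170 main-study subjects, and to up to 80 training subjects, whose AEs are summarised under 10.1: 170 + 80 = 250. This counts subjects to whom the rule applies, not events lost.

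**The case against.** The strongest reply is that little is lost, for four reasons.

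1. *Serious events have their own protection.* This stands. A reader might infer that a serious deterioration could go unreported, but 8.1.2, the SAE paragraph of 8.3 and 8.4.2 all require serious events to be reported, 8.1.2 expressly whatever the investigator thinks of relatedness.
2. *The doubt rule in 8.2.2 makes uncertain cases default to reporting.* This stands for uncertain cases. It does not help where the investigator is confident that the worsening is unrelated, because 8.3 then says plainly that it is not an AE.
3. *Worsening is still observed.* NOSE (7.2.1), VAS (7.2.2), nasal examination (7.2.8), obstruction-related doctor visits (7.2.5), medications (7.5) and allergic rhinitis status (4.2.3) are collected whatever the cause. This stands: the observation is largely kept. What is missing is the event record, with onset, severity, relationship and outcome, on which 10.4.4 depends.
4. *Relatedness is a legitimate limit elsewhere.* This also stands. Section 8.1 uses it for non-serious events outside the head/neck and respiratory systems, and 7.1.5 uses it after month 12. The statement in 8.2.2 is therefore not absolute. But neither limit covers head/neck and respiratory worsening before month 12.

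Two further inferences are tempting and unsupported. One is that the Medical Monitor would otherwise have reclassified such events as related. Under 8.2.2 the investigator assigns causality, and under 8.2.3 and 8.6 the Medical Monitor judges expectedness and reviews AEs; no provision describes overturning causality. Only the narrower point holds, that an unrecorded event is not reviewed. The other is that rhinitis or sinus disease is especially likely to worsen after this procedure. Neither is among the risks in 2.3.2.

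**Conclusion.** The contradiction is real, and nothing else in the document resolves it. The 8.3 sentence is wrong as written, not merely short of detail, and should be corrected.

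The definite effect is confined to one class of event and, as a result, the incidences in 10.4.4 understate all-cause events in that class. The effect on the primary safety endpoint is conditional on investigator misjudgement. The number of events affected cannot be derived from the documents, and it would be wrong to read the reach of the rule as a size of loss.

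This rests on two readings: that the 8.3 exception is exclusive, and that 7.1.5 governs non-serious events after month 12. If the general wording of 8.3 on events during the course of the study governed instead, the loss would extend beyond month 12.

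**What to change.** Replace the relatedness condition in 8.3 with wording that carries the scope, for example: *If a baseline condition deteriorates, and the deterioration falls within the collection scope of Section 8.1 (any SAE; any head/neck or respiratory event; any other event related to device or procedure) and within the applicable collection period, it will be recorded as an AE, and the relationship of the deterioration will then be graded under Section 8.2.2.*

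Deleting the relatedness phrase alone would not do. Every deterioration in any system at any time would then be recorded, in conflict with the scope in 8.1 and the month-12 limit in 7.1.5.

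Two details should be settled in the same edit. For the collection period, cite 7.1.5 for non-serious events and reconcile it with 8.1 for serious ones, since 8.1 collects SAEs to the end of participation while 7.1.5 restricts collection to adverse device effects after month 12. The text should also say whether a worse NOSE score alone counts as a deterioration, because the plan does not separate lack of benefit from an adverse event.

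The cost is a short protocol amendment, some additional event forms and a somewhat higher reported all-AE incidence. The definition of the primary safety endpoint does not change.
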